1.0 Definitions of Terms

1.1 Definitions

Item	Definition
Survey unit period (periodic safety report)	Periodic Safety Report 1: July 22, 2012 to January 21, 2013 Periodic Safety Report 2: January 22, 2013 to July 21, 2013 Periodic Safety Report 3: July 22, 2013 to January 21, 2014 Periodic Safety Report 4: January 22, 2014 to July 21, 2014 Periodic Safety Report 5: July 22, 2014 to July 21, 2015 Periodic Safety Report 6: July 22, 2015 to July 21, 2016 Periodic Safety Report 7: July 22, 2016 to July 21, 2017 Periodic Safety Report 8: July 22, 2017 to July 21, 2018
Drug	Lotriga Granular Capsules
SOC	System organ class of MedDRA.
HLGT	High level group term of MedDRA.
PT	Preferred term of MedDRA.
LLT	Lowest level term of MedDRA.
Enrolled patient	A patient approved for enrollment in the Study.
Patient with eCRF collected	An enrolled patient whose eCRF was submitted via CCI .
Patient with eCRF uncollected	An enrolled patient other than a patient with eCRF collected.
Locked patient	A patient who has completed the approval process in the PMS system.
Unlocked patient	A patient with eCRF collected other than a locked patient.
Safety-evaluable patient	A locked patient included in safety evaluation.
Safety-unevaluable patient	A locked patient excluded from safety evaluation.
Efficacy-evaluable patient	A safety-evaluable patient included in efficacy evaluation.
Efficacy-unevaluable patient	A safety-evaluable patient excluded from efficacy evaluation.
ADR	An abbreviated form of the term ‘adverse drug reaction or infection.’ Refers to an adverse event other than those judged by the investigator as ‘not related’ in causality to the Drug. In this plan, ‘adverse drug reactions or infections’ is used in headings, and ‘ADRs’ is used in the text and tables.
Serious adverse event (SAE)	[Prior-approval data] An adverse event (AE) judged as ‘serious’ by the trial investigator. [Surveillance data] An adverse event (AE) judged as ‘serious’ by the investigator. Note that events listed in the separate MedDRA code list of the Takeda Medically Significant AE List should be treated as serious even if judged as

Item	Definition
	'not serious' by the investigator.
Bleeding-related event	An event falling under Standardized MedDRA Query (SMQ) code 20000038 (hemorrhagic SMQ [narrow scope]).

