Rate of patients	
[For safety compilation with safety-evaluable patients] Calculated by the following equation: $[\text{Number of Patients}] / [\text{Number of Safety-Evaluable Patients}] \times 100$.
 
[For safety compilation with safety-unevaluable patients] Calculated by the following equation: $[\text{Number of Patients}] / [\text{Number of Safety-Unevaluable Patients}] \times 100$.

Onset time	
Calculated by the following equation: $[\text{Onset Date}] - [\text{Start Date}] + 1$.
 
If the onset date is unknown, use the first day of the month as the onset date in this equation. However, use the start date as the onset date if $[\text{Start Year \& Month}] = [\text{Onset Year \& Month}]$.

Liver patient	A patient with 'fatty liver,' 'alcoholic fatty liver,' 'chronic hepatitis' or 'hepatic cirrhosis' check-marked in the Complication Details field. Or a patient with a complication falling under the SMQ code 20000005 (hepatic SMQ [narrow scope]) in the Complication Details (Other Diseases) field.
Kidney patient	A patient with 'diabetic nephropathy,' 'glomerulonephritis' or 'chronic kidney disease (CKD)' check-marked in the Complication Details field. Or a patient with a complication falling under the Takeda MedDRA query (TMQ) (Renal Disease) in the Complication Details (Other Diseases) field.
Heart patient	A patient with 'myocardial infarction,' 'angina pectoris' or 'atrial fibrillation' check-marked in the Complication Details field. Or a patient with a complication falling under the SOC code 10007541 (cardiac disorders) in the Complication Details (Other Diseases) field.
Cerebrovascular patient	A patient with 'cerebral infarction' or 'cerebral hemorrhage' check-marked in the Complication Details field. Or a patient with a complication falling under the SMQ code 20000060 (cerebrovascular SMQ [narrow scope]) in the Complication Details (Other Diseases) field.
Diabetic patient	A patient with 'diabetes' check-marked in the Complication Details field. Or a patient with a complication falling under the TMQ code (Diabetes Mellitus Confirmed diagnosis, excl diagnostics) in the Complication Details (Other Diseases) field.
Hypertensive patient	A patient with 'hypertension' check-marked in the Complication Details field. Or a patient with a complication falling under the SMQ code 20000147 (hypertensive SMQ [narrow scope]) in the Complication Details (Other Diseases) field.

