Myocardial infarction	A patient with 'myocardial infarction' check-marked in the Complication

Item	Definition
patient	Details field. Or a patient with a complication falling under the SMQ code 20000047 (myocardial infarction SMQ [narrow scope]) in the Complication Details (Other Diseases) field.
Anginal patient	A patient with ‘angina pectoris’ check-marked in the Complication Details field. Or a patient with a complication falling under the MedDRA PT code 10002383 (angina pectoris), 10002388 (unstable angina pectoris), 10036759 (Prinzmetal angina), or 10058144 (postinfarction angina) in the Complication Details (Other Diseases) field.
Atrial fibrillation patient	A patient with ‘atrial fibrillation’ check-marked in the Complication Details field. Or a patient with a complication falling under the MedDRA PT code 10003658 (atrial fibrillation) in the Complication Details (Other Diseases) field.
Ischemic cerebrovascular patient	A patient with ‘cerebral infarction’ check-marked in the Complication Details field. Or a patient with a complication falling under the SMQ code 20000063 (ischemic cerebrovascular disease SMQ [narrow scope]) in the Complication Details (Other Diseases) field.
Hemorrhagic cerebrovascular patient	A patient with ‘cerebral hemorrhage’ check-marked in the Complication Details field. Or a patient with a complication falling under the SMQ code 20000064 (hemorrhagic cerebrovascular disease SMQ [narrow scope]) in the Complication Details (Other Diseases) field.
Bleeding-related event patient	A patient with a complication falling under the SMQ code 20000038 (bleeding SMQ [narrow scope]) in the Complication Details (Other Diseases) field.
Age	
Calculated by the following equation: [Start Year] - [Birth Year] - 1 if [Start Month & Day] < [Birth Month & Day].
 
Calculated by the following equation: [Start Year] - [Birth Year] if [Start Month & Day] ≥ [Birth Month & Day].
 
If the birth day is unknown, use the first day of the month instead in this equation.

BMI	Calculated by the following equation: [Weight (kg)] / (0.0001 × [Height (cm)] × [Height (cm)]). Indicated by rounding off to the first decimal place.
Disease duration (in years)	Calculated by the following equation: ([Start Year & Month] - [Year & Month of Hyperlipidemia Diagnosis] + 1) / 12. Indicated by rounding off to the first decimal place.
Start date	The start date of first administration of the Drug stated in the Treatment Duration field of the eCRF.

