2.1 Patient Breakdown (Patient Disposition)

Statistical Analysis Set	Enrolled patients in this special drug use surveillance
Details of Statistical Analysis	
Number of enrolled patients, number of patient enrollment sites, number of patients with eCRFs collected, number of patients with eCRFs uncollected, number of locked patients, number of unlocked patients, number of safety-evaluable patients, number of safety-unevaluable patients, number of efficacy-evaluable patients, number of efficacy-unevaluable patients
 
Do not double-count the same medical institution with different participating clinical departments when counting the number of patient enrollment sites.
 
Count the number of patients per reason below for not collecting and total the numbers when the number of patients with eCRFs uncollected.
 
<Reasons for not collecting>
 
 • Survey under way • eCRFs uncollectable • Investigator transferred • Investigator’s health reasons • Patients enrolled 15 days after Drug prescription [before eCRF collection] • Others 
Count the number of patients per reason below for exclusion and total the numbers when counting the numbers of safety- and efficacy-unevaluable patients. If the same patient falls under multiple reasons for exclusion, they should be counted separately.
 
<Reasons for exclusion from safety evaluation>
 
 • Drug administered before contract period • Patient enrolled 15 days after Drug prescription • No data available after Drug administration • Drug not administered 
<Reasons for exclusion from efficacy evaluation>
 
 • Other than target disease • Exclusion criteria violation 
No output needs to be generated for items for which the number of patients is zero.
 
For periodic safety reports, the numbers of efficacy-evaluable and unevaluable patients should not be counted.

Figure/Table No.	Figure 2.1, Table 2.1

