Item Name	Category																							
Sex	Male, Female																							
Age	Summary statistics																							
	Minimum age to 64 years, 65 to 74 years, 75 years to maximum age, Unknown																							
Treatment category	Outpatient, inpatient																							
BMI	Summary statistics																							
	Less than 18.5 kg/m ² , 18.5 to less than 25 kg/m ² , 25 to less than 30 kg/m ² , 30 kg/m ² or over, unknown																							
Complications	No, Yes																							
Complication breakdown	Hypertension, Diabetic, Liver disorder, Kidney disorder, Cardiac disorders [myocardial infarction, angina pectoris, atrial fibrillation, others], Cerebrovascular diseases [hemorrhagic cerebrovascular disease, ischemic cerebrovascular disease, others], Bleeding-related event, Others																							
Drinking history (Does the patient drink alcoholic beverages nearly every day?)	Yes, No, Unknown																							
Fasting triglyceride at baseline (mg/dL)	Less than 150 mg/dL, 150 to less than 400 mg/dL, 400 to less than 500 mg/dL, 500mg/dL or over, Not measured																							
	Less than 150 mg/dL, 150 to less than 400mg/dL, 400 to less than 500 mg/dL, 500 to less than 750 mg/dL, 750 mg/dL or over, Not measured																							
Random triglyceride at baseline (mg/dL)	Less than 150 mg/dL, 150 to less than 400 mg/dL, 400 to less than 500 mg/dL, 500mg/dL or over, Not measured																							

		Less than 150 mg/dL, 150 to less than 400mg/dL, 400 to less than 500 mg/dL, 500 to less than 750 mg/dL, 750 mg/dL or over, Not measured
	Smoking history	Never, Current, Former, Unknown
	Hypersensitivity disposition	No, Yes, Unknown
	Disease duration	Summary statistics
		Less than 1 year, 1 to less than 3 years, 3 to less than 5 years, 5 years or over, Unknown
	Presence or absence of surgery within one month before baseline	No, Yes
	Pregnancy status during treatment (only for female)	No, Yes
Figure/Table No.	Table 2.2	

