Details of Statistical Analysis	
Categorize adverse drug reactions (bleeding-related events) by the following categories for each item, and count the types of adverse drug reactions (bleeding-related events). The categories and the compilation method of adverse drug reactions are the same as described in section 2.4.5.

Figure/Table No.	Table 2.4.7

2.4.8 Rate of Patients of Adverse Drug Reactions or Infections by Patient Demographics and Treatment

Details

Statistical Analysis Set	Safety-evaluable patients in this special drug use surveillance	
Details of Statistical Analysis	Categorize ADRs by the following categories for each item and compile the rate of patients with ADRs.	
	Item Name	Category
	Sex	Male, Female
	Age	Minimum age to 64 years, 65 to 74 years, 75 years to maximum age, Unknown
	BMI	Less than 18.5 kg/m ² , 18.5 to less than 25 kg/m ² , 25 to less than 30 kg/m ² , 30 kg/m ² or over, unknown
	Complications	No, Yes
	Complication breakdown	Hypertension, Diabetic, Liver disorder, Kidney disorder, Cardiac disorders Cerebrovascular diseases, Bleeding-related event, Others
	Fasting triglyceride at baseline (mg/dL)	Less than 150 mg/dL, 150 to less than 400 mg/dL, 400 to less than 500 mg/dL, 500mg/dL or over, Not measured
		Less than 150 mg/dL, 150 to less than 400mg/dL, 400 to less than 500 mg/dL, 500 to less than 750 mg/dL, 750 mg/dL or over, Not measured
	Random triglyceride at baseline (mg/dL)	Less than 150 mg/dL, 150 to less than 400 mg/dL, 400 to less than 500 mg/dL, 500mg/dL or over, Not measured
		Less than 150 mg/dL, 150 to less than 400mg/dL, 400 to less than 500 mg/dL, 500 to less than 750 mg/dL, 750 mg/dL or over, Not measured
	Initial dose	2 g, 4 g, other
	Breakdown of presence of change in daily dose	2 g → 4 g, 4 g → 2 g, Other
	Presence or absence of concomitant antihyperlipidemic drug use (during observation period)	No, Yes

	Breakdown of concomitant antihyperlipidemic drugs (during observation period)	statins drugs, fibrate drugs, intestinal transporter inhibitors, anion-exchange resin, nicotinic acid derivatives, probucol, ethyl icosapentate (EPA), others
	Presence or absence of concomitant anticoagulant/antiplatelet drug use (during observation period)	No, Yes
	Breakdown of concomitant anticoagulant/antiplatelet drugs (during observation period)	Anticoagulant drugs, antiplatelet drugs
Figure/Table No.	Table 2.4.8	

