2.4.18 Onset Status of Adverse Drug Reactions or Infections by Presence or Absence of Cerebrovascular Complications

Statistical Analysis Set	Safety-evaluable patients in this special drug use surveillance
Details of Statistical Analysis	Compile ADR types by presence or absence of cerebrovascular complications. The compilation method of ADR types is the same as described in section 2.4.1.
Figure/Table No.	Table 2.4.18

2.4.19 Onset Status of Adverse Drug Reactions or Infections by Presence or Absence of Bleeding-related Event Complications

Statistical Analysis Set	Safety-evaluable patients in this special drug use surveillance
Details of Statistical Analysis	Compile ADR types by presence or absence of bleeding-related event complications. The compilation method of ADR types is the same as described in section 2.4.1.
Figure/Table No.	Table 2.4.19

2.4.20 Onset Status of Adverse Drug Reactions or Infections by Presence or Absence of Concomitant Anticoagulant and/or Antiplatelet Drugs

Statistical Analysis Set	Safety-evaluable patients in this special drug use surveillance
Details of Statistical Analysis	Compile ADR types by presence or absence of concomitant anticoagulant or antiplatelet drugs (Concomitant anticoagulant / antiplatelet , Anticoagulant only, Antiplatelet only, Neither). The compilation method of ADR types is the same as described in section 2.4.1.
Figure/Table No.	Table 2.4.20

2.4.21 Onset Status of Adverse Drug Reactions (Bleeding-Related Events) by Presence or Absence of Concomitant Anticoagulant and/or Antiplatelet Drugs

Statistical Analysis Set	Safety-evaluable patients in this special drug use surveillance
Details of Statistical Analysis	Compile the types of adverse drug reactions (bleeding-related events) by presence or absence of concomitant anticoagulant or antiplatelet drugs (Concomitant anticoagulant / antiplatelet , Anticoagulant only, Antiplatelet only, Neither). The compilation method of the types of adverse drug reactions is the same as described in section 2.4.1.
Figure/Table No.	Table 2.4.21

2.4.22 Onset Status of Adverse Drug Reactions or Infections by Baseline Fasting Triglyceride Level

Statistical Analysis Set	Safety-evaluable patients in this special drug use surveillance whose fasting triglyceride levels were measured at baseline

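### The SAP's definition of a bleeding-related event patient omits the check-mark field, so a cerebral hemorrhage recorded only by check-mark is counted as bleeding absent in Table 2.4.19

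*SAP*

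**What the plan says.** SAP 1.1 (Definitions) sets out twelve complication groups. Eleven have two branches joined by an 'or': a check-marked item in the Complication Details field, or a coded term in the separate Other Diseases field. For the hemorrhagic cerebrovascular group the item in the first branch is cerebral hemorrhage, and the definition runs: "check-marked in the Complication Details field. Or a patient with a complication falling under the SMQ code 20000064 (hemorrhagic cerebrovascular disease SMQ [narrow scope"]). The cerebrovascular group takes cerebral infarction or cerebral hemorrhage as its first-branch items, and its definition runs: "check-marked in the Complication Details field. Or a patient with a complication falling under the SMQ code 20000060 (cerebrovascular SMQ [narrow scope"]).

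The bleeding group has the second branch only: "A patient with a complication falling under the SMQ code 20000038 (bleeding SMQ [narrow scope]) in the Complication Details (Other Diseases) field". The same query code defines a bleeding-related event elsewhere in SAP 1.1, where it is labelled hemorrhagic: "An event falling under Standardized MedDRA Query (SMQ) code 20000038 (hemorrhagic SMQ [narrow scope"]).

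The bleeding group is used in three places:

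- SAP 2.4.19: "Compile ADR types by presence or absence of bleeding-related event complications".
- The complication breakdown of SAP 2.2: "Cerebrovascular diseases [hemorrhagic cerebrovascular disease, ischemic cerebrovascular disease, others], Bleeding-related event, Others".
- The complication breakdown of SAP 2.4.8: "Cerebrovascular diseases, Bleeding-related event, Others".

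Protocol 4.0, exclusion criterion (1), bars patients with hemorrhage. In SAP 2.1, "Exclusion criteria violation" is listed as a reason for exclusion from efficacy evaluation only.

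**The concern.** A diagnosis should fall in the same stratum wherever on the form it was entered. Here a hemorrhagic term written under Other Diseases puts the patient in the bleeding group, while the check-mark for cerebral hemorrhage does not. The check-mark is the more direct way to record that condition.

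In Table 2.4.19 the definition acts as a presence/absence stratifier, so the misfiled patient is not merely omitted but placed with patients who have no bleeding complication. Tables 2.2 and 2.4.8 have no absent row for bleeding; there the patient is missing from the bleeding count but still appears under cerebrovascular disease. Table 2.2 could then show more hemorrhagic cerebrovascular patients than bleeding patients. Bleeding is the protocol's priority survey item (Protocol 9.6 and 10.4.1), so an inconsistency of this kind is likely to be noticed.

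**Working it through.** The plan states no figure on this point, so there is none to reproduce. The check has three steps.

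**1. Count the definitions in SAP 1.1.** With a check-mark branch: liver, kidney, heart, cerebrovascular, diabetic, hypertensive (6), plus myocardial infarction, angina, atrial fibrillation, ischemic cerebrovascular, hemorrhagic cerebrovascular (5), which makes 11. Without one: bleeding-related event (1).

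**2. Apply the rules to each way of recording a cerebral hemorrhage.** The Other Diseases entry is taken to be a cerebral hemorrhage term covered by both queries.

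| Check-mark | Other Diseases term | Hemorrhagic cerebrovascular | Bleeding, as written | Bleeding, with a check-mark branch |
|---|---|---|---|---|
| no | no | absent | absent | absent |
| no | yes | present | present | present |
| yes | no | present | **absent** | present |
| yes | yes | present | present | present |

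One cell is discordant: check-mark only. Nothing elsewhere in the SAP says that check-marked items are also carried into Other Diseases, and the 'or' in the eleven paired definitions treats the two fields as separate sources.

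Nor does eligibility empty that cell. The four reasons for exclusion from safety evaluation in SAP 2.1 are administration before the contract period, late enrollment, no data after administration, and drug not administered. None concerns the exclusion criteria, so a patient who violates criterion (1) stays in the safety tables.

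**3. Size, by illustration.** Let k be the patients recorded by check-mark only and m those recorded under Other Diseases. The documents give neither. The assumed ranges are k = 3 to 15 (0.1% to 0.5% of the 3,000 target in Protocol 3.1) and m = 5 to 30.

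Share of the presence column lost = k/(k + m):

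| | m = 5 | m = 30 |
|---|---|---|
| k = 3 | 3/8 = 38% | 3/33 = 9% |
| k = 15 | 15/20 = 75% | 15/45 = 33% |

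If k = 0 nothing is lost.

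Shift in the ADR rate of the absence column = k × (rate in misplaced patients − rate in the rest)/(3,000 − m). Take 9.6% for the rest (the pre-approval ADR rate in Protocol 1.0) and assume double that, 19.2%, in the misplaced patients:

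- k = 3, m = 5: 3 × 9.6/2,995 = 0.01 percentage points.
- k = 15, m = 30: 15 × 9.6/2,970 = 0.05 percentage points.

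The presence-column rate would differ from its correct value by [k/(k + m)] × (rate in check-mark-only patients − rate in the others with bleeding complications). This is zero if the two subgroups share a rate. If they differed by 9.6 points (again an assumption), it would be 0.09 × 9.6 = 0.9 to 0.75 × 9.6 = 7.2 percentage points.

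**The case against.** The strongest reply has four parts.

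- **Unseen links.** Neither the eCRF page nor the term list of the query is in the documents. That cerebral hemorrhage belongs to query 20000038 is read from the SAP's own labels, hemorrhagic and bleeding. Whether check-marked items are also coded is unknown. This stands as a limit on knowing how many patients are affected; it does not change what the written rule does.
- **Possible intent.** The earliest SAP version in the file has no such definition. It was added later, directly below the hemorrhagic cerebrovascular group, and could have been meant for bleeding conditions without a check-box. The text does not fit that reading: a hemorrhagic cerebrovascular term under Other Diseases counts in both groups, so cerebral hemorrhage is not kept out of the bleeding group as such. If the omission is intended, the SAP needs to say so.
- **Few patients, little lost.** Exclusion criterion (1) should make such patients rare, and a resolved hemorrhage may be recorded as medical history instead. Check-marked cases are still visible in the hemorrhagic cerebrovascular row of Table 2.2 and, pooled, in Tables 2.4.8 and 2.4.18. All this is fair.
- **The 9% to 75% range comes from assumed inputs.** It does, and the upper end needs three times as many check-mark-only patients as all others with bleeding complications. It shows sensitivity and is not an estimate.

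Table 2.4.19 is also descriptive, with no test or interval, and no main conclusion depends on it.

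**Conclusion.** The concern holds. As written, the definition assigns a patient whose cerebral hemorrhage is recorded only by check-mark to the wrong stratum of Table 2.4.19 and leaves that patient out of the bleeding rows of Tables 2.2 and 2.4.8. No other rule in the SAP corrects this. The absence column would hardly change; a small presence column could lose a material share of its patients. The true number is not known and is probably small.

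The conclusion rests on two readings of the text: that query 20000038 covers cerebral hemorrhage, as its labels indicate, and that the Other Diseases field does not already contain the check-marked items. The on-treatment bleeding results (Tables 2.4.7 and 2.4.21) use the event-based definition and are not affected. This should be corrected, but it does not threaten the main safety findings.

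**What to change.** Redefine the group in SAP 1.1 as a patient with cerebral hemorrhage check-marked in the Complication Details field, or with a complication under SMQ 20000038 (narrow scope) in the Complication Details (Other Diseases) field. Check the eCRF for any other hemorrhagic check-mark item and add it to the same clause. If the omission is deliberate, state that and give the reason.

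The cost is one clause in one definition and a rerun of Tables 2.2, 2.4.8 and 2.4.19. The check-mark is already collected and already used for two other groups, so no new data are needed.

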9.4 Testing/Observation Items

1) Survey items

Triglyceride (TG), total cholesterol (TC), LDL cholesterol* (LDL-C), HDL cholesterol (HDL-C), VLDL cholesterol (VLDL-C), Apo-AI, Apo-B, Apo-CIII, lipoprotein (a), remnant lipoprotein cholesterol (RLP-C), fasting blood glucose (FBG), HbA1c

*: When tested by direct measurement

2) Survey timing

Baseline, Month 3, Month 6, Month 9, and Month 12 (or discontinuation of treatment) test timepoints

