10.5 Efficacy Items

Compile the following regarding the efficacy-evaluable population.

10.5.1 Changes in Lipid Parameters: TG, TC, LDL-C, HDL-C, Non-HDL-C, etc.

Tabulate observed values and changes (observed value at each observational timepoint after baseline minus observed value at baseline) at each observational timepoint for TG, TC, LDL-C (by converted value calculated by direct measurement, Friedewald formula*), HDL-C, Non-HDL-C (converted value**), VLDL cholesterol, Apo-AI, Apo-B, Apo-CIII, lipoprotein (a), and RLP-C.

*: $LDL-C = TC - HDL-C - TG / 5$

**: $Non-HDL-C = TC - HDL-C$

Note that LDL-C, Non-HDL-C, TC/LDL-C ratio, LDL-C/HDL-C ratio, and LDL-C/Apo-B ratio should be calculated from test results.

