LDL cholesterol (Friedewald formula) (mg/dL)	Calculated the equation below if the patient is fasting at the time of blood collection for laboratory testing with triglyceride 400 mg/dL or over. Indicated by rounding off to an integer alone. Total cholesterol - HDL cholesterol - triglyceride / 5
Non-HDL cholesterol (mg/dL)	Calculated by the equation below if triglyceride is 400 mg/dL or over. Indicated by rounding off to an integer alone. Total cholesterol - HDL cholesterol

Item	Definition
TC/HDL-C ratio	Calculated by the equation below. Indicated by rounding off to the first decimal place. Total cholesterol / HDL cholesterol
LDL-C/HDL-C ratio	Calculated by the equation below. Indicated by rounding off to the first decimal place. LDL cholesterol (Friedewald formula) / HDL cholesterol
LDL-C/Apo-B ratio	Calculated by the equation below. Indicated by rounding off to the first decimal place. LDL cholesterol (Friedewald formula) / Apo-B (fasting)
Summary statistics	Number of patients, mean value, standard deviation, minimum value, first quartile, median, third quartile, maximum value

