2.5 Efficacy Statistical Analysis

2.5.1 Changes in Laboratory Test Values (Fasting Lipid)

Statistical Analysis Set	Efficacy-evaluable patients in this special drug use surveillance
Details of Statistical Analysis	Calculate summary statistics at each evaluation timepoint for fasting measurements and rates of change from baseline (%) of triglyceride (mg/dL), LDL cholesterol (Friedewald formula) (mg/dL), VLDL cholesterol (mg/dL), VLDL cholesterol (%), Apo-B (mg/dL), Apo-CIII (mg/dL), lipoprotein(a) (mg/dL), and remnant lipoprotein cholesterol (mg/dL). In addition, calculate the 95% confidence interval for the mean value for rates of change from baseline (%).
Figure/Table No.	Table 2.5.1

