2.5.3 Changes in Laboratory Test Values (Lipid)

Statistical Analysis Set	Efficacy-evaluable patients in this special drug use surveillance
Details of Statistical Analysis	Calculate summary statistics at each evaluation timepoint for random measurements and rates of change from baseline (%) of total cholesterol (mg/dL), LDL cholesterol (direct measurement) (mg/dL), HDL cholesterol (mg/dL), non-HDL cholesterol (mg/dL), Apo-AI (mg/dL). In addition, calculate the 95% confidence interval for the mean value for rates of change from baseline (%).
Figure/Table No.	Table 2.5.3

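### SAP 1.1 calculates Friedewald LDL-C and non-HDL-C only when triglyceride is 400 mg/dL or over; protocol 10.5.1 sets no such limit

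*SAP*

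**What the plan says.** SAP 1.1 (Definitions) derives Friedewald LDL-C "if the patient is fasting at the time of blood collection for laboratory testing with triglyceride 400 mg/dL or over". For non-HDL-C the entry reads "Calculated by the equation below if triglyceride is 400 mg/dL or over". Neither entry says what happens below 400 mg/dL. The three older SAP versions in the same file carry the same two conditions.

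The LDL-C/HDL-C ratio is defined as "LDL cholesterol (Friedewald formula) / HDL cholesterol", and LDL-C/Apo-B also takes the Friedewald value as its numerator.

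Protocol 10.5.1 gives "LDL-C = TC - HDL-C - TG / 5" and "Non-HDL-C = TC - HDL-C" with no TG condition, and asks for LDL-C, non-HDL-C and the LDL-based ratios to be calculated from the test results. Protocol 9.4 qualifies the collected LDL-C with the footnote "When tested by direct measurement".

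The derived variables feed three outputs, none of which mentions a TG restriction:

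- Table 2.5.1: percent change in Friedewald LDL-C.
- Table 2.5.3: percent change in "LDL cholesterol (direct measurement) (mg/dL), HDL cholesterol (mg/dL), non-HDL cholesterol (mg/dL), Apo-AI (mg/dL".
- Table 2.5.4: the ratios at each timepoint.

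**The concern.** LDL-C and non-HDL-C are named efficacy variables in protocol 10.5.1, and the SAP's condition decides who has a value. The SAP expects patients below the threshold: its baseline TG strata in 2.2, 2.5.5 and 2.5.6 include below 150 and 150 to below 400 mg/dL. Samples in that range would have neither derived cholesterol value and neither LDL-based ratio. Direct LDL-C cannot fill the ratios, because they are defined on the Friedewald value. A patient with no direct test and TG below 400 has no LDL-C at all.

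The percent-change tables have a second problem. A change needs a value at both visits, so it exists only where TG was at least 400 at baseline and stayed there. For a TG-lowering drug, patients who respond well are the ones removed. Table 2.5.4 reports values without changes, so it loses samples below 400 but has no paired selection.

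**Working it through.** **Inputs from the documents.** The two formulas (the same in SAP 1.1 and protocol 10.5.1), the 400 mg/dL floor (SAP 1.1 only), and the baseline TG strata. The plan gives no figure to reproduce on this point.

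**1. Non-HDL-C.** TC − HDL-C has no TG term. With assumed TC 230 and HDL-C 40 mg/dL it is 230 − 40 = 190 at every TG. The condition changes only who has a value.

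**2. Friedewald LDL-C.** The subtracted term is TG/5: 150/5 = 30, 400/5 = 80, 750/5 = 150 and 1000/5 = 200 mg/dL. Under the SAP rule every calculated value subtracts at least 80 mg/dL, and samples with a smaller term are dropped. With the same assumed TC and HDL-C:

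| TG (mg/dL) | 230 − 40 − TG/5 |
|---|---|
| 400 | 110 |
| 750 | 40 |
| 950 | 0 |
| 1000 | −10 |

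**3. Loss during follow-up.** A patient starting at B ≥ 400 loses the on-treatment value once TG falls by more than 1 − 400/B: 11.1% from 450, 20.0% from 500, 33.3% from 600 and 46.7% from 750 mg/dL.

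**4. Share of patients with a value.** The documents give no TG distribution, so this step is illustrative. Assumptions: fasting TG log-normal, median m = 200-300 mg/dL, log-SD s = 0.5-0.6, geometric fall 20%, SD of the log-ratio 0.4.

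The share with a baseline value is 1 − Φ(ln(400/m)/s):

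- m = 200, s = 0.5: ln 2/0.5 = 1.386, giving 0.083.
- m = 300, s = 0.6: ln(4/3)/0.6 = 0.479, giving 0.316.
- m = 400 gives 0.50, so the majority is excluded whenever the median is below 400.

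Paired shares come from simulating 4,000,000 pairs of visits. Model A has the same log-SD at both visits, with correlation 1 − 0.16/(2s²). Model B has a log-ratio independent of baseline, with correlation s/√(s² + 0.16).

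| | Model A | Model B |
|---|---|---|
| Correlation between visits | 0.68-0.78 | 0.78-0.83 |
| TG ≥ 400 at both visits (SAP rule) | 1.9-15.8% | 4.1-19.4% |
| Geometric TG change in those kept | −9.4% to −13.6% | +7.1% to −1.7% |
| TG < 400 at both visits (reversed rule) | 64.5-90.2% | 63.8-88.2% |
| Geometric TG change in those kept | −16.7% to −18.7% | −22.1% to −24.0% |

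The change in everyone is −20% by construction. A separate run with correlation 0.6, log-SD 0.4-0.6 and a 10-30% fall gave about 0.2-16% at or above 400 at both visits, and 59-96% below 400 at both.

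These shares are for fasting Friedewald LDL-C. They do not carry over to non-HDL-C, whose condition has no fasting requirement and whose table specifies random measurements.

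**The case against.** **The direction is inferred.** The documents state no validity limit for the Friedewald formula. A growing TG/5 term does not prove that 400 is a ceiling, and the negative example holds TC fixed by assumption. This stands, which is why the text says the rule appears reversed. It does not affect non-HDL-C, where the formula alone shows the condition has no function, nor the contradiction with the protocol.

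**The reversed rule also loses patients.** Three of the five measured strata lie at 400 or over and would have no baseline Friedewald value, against two under the current text. True, but a count of strata is not a count of patients.

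**The condition works per sample.** A patient below 400 at baseline and at or above 400 later still gets a follow-up value, about 1.5-5.4% of patients under models A and B. Such a patient still has no change from baseline.

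**Direct LDL-C remains.** It is on the schedule at every visit, and Table 2.5.3 reports it without a TG condition. This mitigates the LDL-C loss to an unknown degree, since it is collected only where the direct test was done. It does nothing for non-HDL-C or the two ratios.

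**Bias is shown in TG, not in LDL-C or non-HDL-C.** Correct. The figures show that retained patients are selected on response; they do not estimate the resulting bias in LDL-C or non-HDL-C.

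**Low stakes, or a wording slip.** The surveillance is descriptive, with no test or decision rule on these variables, and the code may be right. Even so, the SAP is the governing text, and a corrected inequality would still leave a purposeless condition on non-HDL-C.

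**Conclusion.** The concern holds. As written, SAP 1.1 contradicts protocol 10.5.1 and withholds two named efficacy variables, and two ratios, from every sample with TG below 400 mg/dL. It also limits percent changes to patients whose TG is at least 400 at both visits. That much follows from the text and the formulas alone.

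The number of patients affected depends on assumptions. Under those set out above, 8-32% have a baseline Friedewald LDL-C and 2-19% a paired change. In both models the retained patients show a smaller TG fall than the assumed 20%. No share is estimated for non-HDL-C. TG, TC, HDL-C, direct LDL-C, Apo-B and TC/HDL-C are unaffected. This should be corrected before Tables 2.5.1, 2.5.3 and 2.5.4 are produced or relied on.

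**What to change.** - **Friedewald LDL-C (SAP 1.1):** calculate if the sample is fasting and TG is less than 400 mg/dL; otherwise set to missing.
- **Non-HDL-C (SAP 1.1):** delete the TG condition and calculate TC − HDL-C whenever both are measured.
- **Reconciliation:** protocol 10.5.1 has no TG limit, so record the below-400 limit for Friedewald LDL-C as a documented departure.
- **Code:** check the derivation program against the corrected text before running the three tables.
- **Reporting:** give the number of samples excluded for TG of 400 or over at each timepoint, and read Friedewald LDL-C alongside direct LDL-C.

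The cost is two lines of SAP wording, one line of reconciliation and a code check, with no new data. The drawback is that patients at 400 or over at baseline have no Friedewald change, and mild selection on later TG remains. Under the same assumptions 64-90% keep a paired change, with a TG change of −17% to −24% against −20% overall.
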